5.4 Analysis Groups

Tables are displayed by treatment group (PXVX0317 and placebo) columns with lots pooled with the exception of the lot consistency analysis, where the separate lots are displayed.

5.5 Analysis Time Points

For immunogenicity analyses, anti-CHIKV SNA samples are collected at Day 1 (baseline), Day 8 (-1/+3 days), Day 15 (-1/+3 days), Day 22 (-1/+3 days) and Day 183 EOS (-14/+7 days). For the purpose of IEP membership, Day 22 has a wider window of Day 19 through Day 27, inclusive. For the time points other than the primary analysis (Day 22), all available data are included in the summaries according to the analysis set defined for a participant's inclusion.

Immunogenicity data are checked and, if another visit or unscheduled sample collection occurred closer to the nominal study day than the scheduled sample collection entered as the nominal visit, the visit data are replaced by the closer visit data when the analysis visit is assigned. In other words, the labeled database visit may not match the derived analysis visit; this procedure is necessary to mitigate the risk of data entered in an incorrect visit in the database. See also Section 5.7 describing handling of multiple sample collections in an analysis window.

Otherwise, unscheduled visit data are not presented in the by-visit summary analyses but are included in the summary tables by maximum toxicity grade or abnormality when applicable, and in data listings by participant.

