
- Review e-diary.
- Solicited AE, unsolicited AE, MAAE, SAE, and AESI evaluation.
- Review concomitant medications.
- Blood collection for anti-CHIKV SNA.
- Directed physical exam (as needed).

5.2.4 Day 15 (-1/+3) Visit 4

- Unsolicited AE, MAAE, SAE, and AESI evaluation.
- Review concomitant medications.
- Blood collection for anti-CHIKV SNA.
- Directed physical exam (as needed).

5.2.5 Day 22 (-1/+3) Visit 5

- Unsolicited AE, MAAE, SAE, and AESI evaluation.
- Review concomitant medications.
- Blood collection for anti-CHIKV SNA.
- Directed physical exam (as needed).

5.2.6 Day 29 (±1) Telephone Contact for Visit 6

- Unsolicited AE, MAAE, SAE, and AESI evaluation.
- Review concomitant medications.

5.2.7 Day 92 (±3) Telephone Contact for Visit 7

- SAE, AESI, and MAAE evaluation.
- Review concomitant medications (only if associated with SAE/AESI/MAAE).

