5.3 Analysis Populations

Analysis are based on the following study populations:

Randomized Population: All screened participants who provide informed consent (and assent for adolescent participants 12 to <18 years of age) and provide demographic and other screening measurements and are randomized (i.e., have a randomization number assigned within the EDC system). Most baseline summaries and the IP administration summary use the randomized population.

Exposed Population: All participants in the randomized population who receive IP.

Safety Population: All participants in the exposed population who provide safety assessment data. This generally includes any participant who was not lost to follow-up at Day 1 (baseline), as they are at risk for reporting an SAE. Participants are analyzed as treated (i.e., according to the treatment a participant received, rather than the treatment to which the participant was randomized). All safety analyses use the safety population.

Modified Intent-to-Treat (mITT) Population: All randomized participants who are vaccinated and have at least one post-injection anti-CHIKV human SNA assay result. Participants are counted in the group to which they were randomized. Primary and secondary

immunogenicity analyses are repeated for the mITT population as a measure of robustness of the results.

Immunogenicity Evaluable Population (IEP): The IEP includes all participants in the mITT population who:

- Provide evaluable serum sample results for the relevant post-vaccination time points, and within the required time frames:
 - Day 22: Day 19 through Day 27, inclusive.
- Have no measurable (*ELLOQ*) anti-CHIKV human SNA assay titer at Day 1 (baseline), i.e., seronegative at baseline. Note that participants with missing Day 1 (baseline) are excluded from IEP.
- Have no important protocol deviation deemed exclusionary or other reason to be excluded as defined prior to unblinding.

The IEP is the primary population for all immunogenicity analyses.

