5.7 Multiple Records in an Analysis Window

If more than one sample is collected for anti-CHIKV human SNA assay assessment for a given time point, the sample closest to the nominal time point is used for analysis tabulations. If there is a tie (i.e., the two samples are an equidistant number of days from the nominal time point), then the geometric mean of the two titers is used for analysis tabulations. All samples are reported with database visit and analysis visit in data listings by participant.

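### SAP 5.5 lets a closer draw from another visit replace a correctly labelled, in-window Day 22 sample; it needs a window limit and a rule that each sample serves one visit

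*SAP*

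**What the plan says.** SAP 5.5 (Analysis Time Points) checks the immunogenicity data and, "if another visit or unscheduled sample collection occurred closer to the nominal study day than the scheduled sample collection entered as the nominal visit", states that "the visit data are replaced by the closer visit data when the analysis visit is assigned". The reason given is that "this procedure is necessary to mitigate the risk of data entered in an incorrect visit in the database".

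Three other provisions bear on how this works:

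- **Collection windows.** The Protocol visit list gives "5.2.4 Day 15 (-1/+3) Visit 4", so Days 14 to 18. Visit 5 has the same tolerance around Day 22, so Days 21 to 25. SAP 5.5 repeats both windows.
- **IEP window.** SAP 5.3 accepts a wider range for the primary time point: "Day 22: Day 19 through Day 27, inclusive". The mITT population requires only some post-injection titer and has no Day 22 window.
- **Several samples.** SAP 5.7 begins "If more than one sample is collected for anti-CHIKV human SNA assay assessment for a given time point" and takes the closest one. For samples equally far from the nominal day, "then the geometric mean of the two titers is used for analysis tabulations".

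For time points other than Day 22, SAP 5.5 includes all available data. A late Visit 4 draw is therefore still a Day 15 value.

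**The concern.** The stated aim is to repair mislabelled samples, but the operative test is closeness alone. It does not ask whether either sample was mislabelled. It does not require the substitute to lie in the window of the visit it fills. It does not say that a sample may serve one visit only. A correctly labelled Visit 5 sample that satisfies the IEP window can therefore lose its place to the Visit 4 draw.

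The Day 22 titer feeds all three coprimary endpoints: seroresponse difference, GMT comparison and lot GMT ratios. Where the rule triggers with a substitute drawn before Day 19, the SAP also leaves open whether the participant is in the primary population. Two programmers could follow the text and produce different IEPs and different Day 22 values.

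**Working it through.** **Inputs.** Nominal Day 22. Protocol windows: Visit 4 Days 14-18, Visit 5 Days 21-25 (Protocol 5.2.4 and 5.2.5; SAP 5.5). IEP window: Days 19-27 (SAP 5.3).

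**Rule.** For a Visit 4 draw on day a (before Day 22) and a Visit 5 draw on day b (after Day 22), Visit 4 is closer when 22 - a < b - 22, that is, when a + b > 44. The two are equidistant when a + b = 44. A Visit 5 draw on Days 19-22 is never displaced by an earlier Visit 4 draw.

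| Visit 4 | Visit 5 | Pairs | Visit 4 closer | Equidistant |
|---|---|---|---|---|
| Days 14-18 (on time) | Days 21-25 (protocol window) | 25 | none | none |
| Days 14-18 (on time) | Days 19-27 (IEP window) | 45 | 18/27 | 17/27, 18/26 |
| Days 19-20 (late) | Days 21-25 (protocol window) | 10 | 20/25 | 19/25, 20/24 |
| Days 19-20 (late) | Days 26-27 | 4 | 19/26, 19/27, 20/26, 20/27 | none |

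The first row follows at once: the largest sum is 18 + 25 = 43, below 44. These are counts of day pairs, not frequencies of participants.

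**The Day 18/Day 27 case.** Distances are 4 and 5 days, so the Day 27 titer is replaced. There are three readings:

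1. IEP membership is judged on the Visit 5 sample first. The participant is in the IEP and contributes a Day 18 titer.
2. IEP membership is judged after replacement. The participant is out, although a valid Day 27 sample exists.
3. Each sample gets one analysis visit, the nearest. Day 18 is 3 days from Day 15 and 4 from Day 22, so it stays with Day 15 and the Day 27 sample is kept.

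**The Day 20/Day 25 case.** Distances are 2 and 3 days. Both draws are in the IEP window, so membership is unaffected, but a Visit 5 titer inside its protocol window is discarded. The third reading does not help: Day 20 is 5 days from Day 15 and 2 from Day 22, so the draw would move to Day 22 and compete there.

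**mITT.** A Visit 5 on Day 30 is 8 days from Day 22; an on-time Visit 4 on Day 15 is 7 days away. Read literally, the Day 15 draw becomes the Day 22 value in the robustness analysis.

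**Size, by assumption only.** If a share p of a group is affected and each affected titer is lower by a factor f, the group GMT is multiplied by f^(-p).

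- Assume a log-linear rise from a Day 8 GMT of about 119 to the 1712 reported 28 days after vaccination (Protocol 1.3.2). A Day 18 value in place of Day 27 is then lower by (1712/119)^(9/21) = 3.1-fold.
- The 119 is not in the documents. It is a lognormal fit to 86% at or above 40 and 98% at or above 15 at Day 8, and the 98% is quoted as an upper figure, not for this dose group.
- With p = 2%, also assumed, 3.1^(-0.02) = 0.978, a 2.2% lower GMT. If titers have plateaued, f = 1 and the shift is nil.

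**Context.** The plan's 95% lot-consistency power reproduces: 2 x Phi(0.176/(0.455 x sqrt(2/207)) - 1.96) - 1 = 95.2%. With 270 evaluable per lot (300 less an assumed 10%) it is 98.9%.

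**The case against.** The strongest defence is that the rule exists to relabel misfiled samples, and that SAP 5.5 and 5.7 speak of the analysis visit of a sample in the singular. On that reading a Day 18 draw stays with Day 15 and the Day 27 sample is safe. Every trigger also needs an off-schedule draw: Visit 5 after Day 25 or Visit 4 after Day 18. Significantly out-of-window assessments are listed as important deviations (SAP 5.2.1), and exclusions are settled before unblinding. All of this is fair, and it keeps the practical reach small. But the single-visit reading is nowhere stated as a rule, and it does not resolve the Day 20/Day 25 case.

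Four stronger readings are tempting, and the documents do not support them:

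- **One sample always serves two visits.** This rests on the SAP's silence, and the singular wording can be read against it.
- **The two draws are averaged.** A tie is not closer, so 5.5 does not apply. Averaging comes only from 5.7, which concerns samples for a given time point. It is a possible reading, most plausible when both draws fall in Days 19-27 (19/25, 20/24) and least so for 17/27 and 18/26.
- **An IEP-valid participant is lost in general.** That can follow only when the substitute predates Day 19. In a tie, nothing is lost.
- **Day 22 titers are biased downwards.** A late Visit 5 would usually be replaced by an earlier draw, but a drop requires titers still to be rising. The documents give no titers between 7 and 28 days after the single 40 µg dose. Lower vaccine titers would in any case work against superiority, and randomization should balance any shift across lots.

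**Conclusion.** The point stands as a misfiring rule in a coprimary derivation. Read as written, SAP 5.5 replaces a valid Day 27 sample with a Day 18 sample outside the IEP window, and an in-window Day 25 sample with a late Visit 4 sample from Day 20. It also leaves IEP membership undetermined in the first case. The mITT analysis shares the gap.

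The rule cannot trigger when both visits are inside their protocol windows. The number of participants affected cannot be computed from the documents and is probably small. No coprimary conclusion is likely to change: superiority power is stated as above 99.9%, lot-consistency power has room, and the assumed 2% share gives a GMT shift of 0 to 2.2%. The day arithmetic is exact; the size is illustrative and depends on the assumed kinetics and share. The reason to act is that a primary-endpoint value should not depend on which reading a programmer adopts.

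**What to change.** Amend SAP 5.5, with a matching sentence in 5.7, so that:

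1. Each sample is assigned to one analysis visit only.
2. A correctly labelled scheduled sample inside its own analysis window (Days 19-27 for Day 22) is not replaced by a sample from another scheduled visit. Substitution between scheduled visits is limited to documented visit mislabelling. This also closes the Day 30/Day 15 case in the mITT.
3. An unscheduled or relabelled sample may serve as Day 22 in the IEP only if drawn on Days 19-27. The closest-sample and tie rules of 5.7 then apply only among samples already assigned to that visit under items 1 and 2.
4. A late Visit 4 draw remains the Day 15 value, in keeping with the inclusion of all available data at that time point.
5. IEP membership is determined after analysis-visit assignment.

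The cost is SAP wording and one derivation step. No new data are needed. The change uses collection dates only, so it can be made without titers or treatment codes. The number of participants it touches can be counted blinded from the dates that feed planned Table 14.1.6.

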5.6 Definition of Baseline

For all analyses, the baseline value for each measure is defined as the last non-missing value prior to IP administration. Note that, for some participants for whom randomization system

errors delayed randomization by one calendar day, procedures performed the day before Day 1 were considered acceptable without being repeated on the actual Day 1.

5.7 Multiple Records in an Analysis Window

If more than one sample is collected for anti-CHIKV human SNA assay assessment for a given time point, the sample closest to the nominal time point is used for analysis tabulations. If there is a tie (i.e., the two samples are an equidistant number of days from the nominal time point), then the geometric mean of the two titers is used for analysis tabulations. All samples are reported with database visit and analysis visit in data listings by participant.

5.8 Coding Dictionaries

Medical history and AEs are coded to system organ class (SOC) and preferred term (PT) based on the Medical Dictionary for Regulatory Activities (MedDRA) dictionary version 24.1.

Prior and concomitant medications and vaccines are coded according to the World Health Organization's (WHO) WHODrug Global Dictionary version C32021 to Anatomical Therapeutic Chemical (ATC) classification and preferred drug name.

5.9 Adverse Event Toxicity/Severity Grading

With the exception of redness and swelling, all solicited AEs are graded by the investigator according to severity grading scales from "mild" to "potentially life-threatening." The severity of redness and swelling, recorded as a diameter (mm) in the solicited adverse event diary, are summarized according to categories based on the largest-diameter linear measurement when a local reaction is present:

- Grade 0/absent = 0-24 mm.
- Grade 1/mild = 25-50 mm.
- Grade 2/moderate = 51-100 mm.
- Grade 3/severe = >100 mm.
- Grade 4/potentially life threatening = necrosis or exfoliative dermatitis.

Events reported as not present (0 mm is entered) are reported as Grade 0. Similarly, body temperatures recorded by the participant that are below 100.4° result in fever reported as Grade 0/absent.

Solicited AEs other than redness and swelling and unsolicited AEs are graded by the investigator for severity. The severity grading scales (Grade 1 = mild, Grade 2 = moderate, Grade 3 = severe, Grade 4 = potentially life-threatening) that are used for safety assessment in this study are provided in Appendix I of this document and Section 7.1.7 of the Protocol, based on the *FDA Guidance for Industry: Toxicity Grading Scale for Healthy Adult and Adolescent Volunteers Enrolled in Preventative Vaccine Clinical Trials* (2). Note that AEs that result in death are classified as Grade 4 and indicated as resulting in death.

6 STATISTICAL CONSIDERATIONS

6.1 Statistical Considerations

Data summaries are tabulated by appropriate grouping for each analysis population as specified in Section 5.3.

Continuous endpoints are summarized by descriptive statistics including number of nonmissing observations (n), mean, SD, median, minimum and maximum. In the analysis of the anti-CHIKV SNA data as a continuous variable, anti-CHIKV SNA values are logarithmically transformed (base10), and the GMTs and associated 95% CI for each treatment group are computed by exponentiating the corresponding log-transformed means and two-sided 95% CIs. Categorical variables are summarized by frequency counts (n) and percentages of participants (%) in each category, including missing or unknown when appropriate.

Unless otherwise specified, CIs and hypothesis tests are two-sided with 95% confidence (or one-sided with 97.5% confidence).

The reporting conventions to be applied to all tables, listings and figures are included in a living document that accompanies the table and listing shells. All derivations, statistical analyses, summaries and listings are generated using SAS Version 9.4 or higher (SAS Institute, Inc., Cary, North Carolina, United States).

6.1.1 Seroresponse Rates

The superiority of the immune response to PXVX0317 vaccine over that to placebo is demonstrated at Day 22 by comparing seroresponse rates between the two treatment groups (the percentage of participants with an anti-CHIKV human SNA assay titer **comparison**). Percentages of participants with anti-CHIKV SNA

seroresponse rate and secondary response rates at ≥ 15 and 4-fold rise over baseline are reported with associated two-sided 95% Wilson score method CIs (keyword /BINOMIAL (WILSON) on tables statement). The difference in seroresponse rates between the PXVX0317 and placebo groups is calculated, along with the 95% CI for the difference based on the Newcombe hybrid score method (keyword /RISKDIFF (CL=NEWCOMBE)). The lower bound of the two-sided 95% CI on the difference in seroresponse rates between PXVX0317 and placebo must be Additionally, the null hypothesis of no difference between seroresponse rate percentages is tested using a two-sided chi-square test with alpha=0.05. No multiplicity adjustment is employed, and no covariate adjustment is performed. See Section 6.4 for statistical hypothesis, Section 6.9 for multiplicity considerations, and Section 8.4.1.1 for analysis outputs.

Identical methods will be used for treatment group comparison of seroresponse rates at Days 15, 183, and 8 as well as for lot consistency analysis of seroresponse rates.

The same methods are applied to evaluate treatment group differences in seroresponse rates at Day 22 using the composite seroresponse rate endpoint (see Section 6.3 for definition) if the baseline seropositive (anti-CHIKV SNA titer \geq LLOQ) rate is \geq 10% for the mITT population only.

6.1.2 Geometric Mean Titers and Geometric Mean Fold Increase

The superiority of PXVX0317 vaccine immunogenicity over that of placebo is explored further by comparing Day 22 GMTs derived from a linear model with a one-sided alpha=0.025. The primary model is an analysis of variance (ANOVA), with log₁₀-transformed anti-CHIKV SNA titers (log₁₀) as the dependent variable and treatment group and study site as the fixed effects in the model. No interaction term is used. The adjusted least square means and their 95% CIs calculated based on the ANOVA are back-transformed and reported as the group GMT values. No adjustment for multiplicity is applied. See Section 6.4 for statistical hypothesis, Section 6.9 for multiplicity considerations, and Section 8.4.1.2 for analysis outputs. Identical methods are used for treatment group comparison of GMTs at Days 8, 15, and 183.

Similar methods are applied to test for a significant difference between anti-CHIKV SNA GMTs at Day 22 for PXVX0317 and placebo if the baseline seropositive (SNA titer \geq LLOQ) rate is \geq 10% in the mITT population only, with baseline log-transformed SNA titer as a covariate in the ANCOVA model.

GMFI from baseline (Day 1) to Days 8, 15, 22 and 183 is calculated using the difference from Day 1 in log₁₀-transformed titers as the dependent variable in the ANOVA model. The adjusted least square means and their 95% CIs calculated based on the ANOVA are backtransformed and reported as the group GMFI values. The median, minimum and maximum titers and fold-increases are based on the non-transformed scale.

The GMTs associated with the primary lot consistency objective are also calculated via a linear model for the anti-CHIKV SNA titers collected at Day 22. The primary model is an ANOVA, with log₁₀-transformed anti-CHIKV SNA titers as the dependent variable and vaccine lot and study site as the fixed effects in the model. No interaction term is used. The adjusted least square means and their 95% CIs calculated based on the ANOVA are back-transformed and reported as the vaccine lot GMT values. The ratio of GMTs for the comparison of the three pairs of PXVX0317 lots (A:B, B:C, A:C) is derived from this model. Pairwise equivalence testing on the log₁₀ scale uses two one-sided tests with alpha=0.025 each and no multiplicity adjustment. If for all pairs of vaccine lots, the two-sided 95% CI of the GMT ratio is within [0.667; 1.5] then lot-to-lot consistency is demonstrated. See Section 6.4 for statistical hypothesis, Section 6.9 for multiplicity considerations, and Section 8.4.1.3 for analysis outputs.

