8.3 Study Endpoints

8.3.1 Primary Endpoints

Safety Endpoints:

- Incidence of solicited AEs through Day 8 for PXVX0317 and placebo.
- Incidence of unsolicited AEs through Day 29 for PXVX0317 and placebo.
- Incidence of AESI, MAAEs and SAEs through Day 183 for PXVX0317 and placebo.

Coprimary Immunogenicity Endpoints:

• Difference in anti-CHIKV SNA seroresponse rate (PXVX0317 minus placebo) and associated 95% CI at Day 22.

Success criterion: Lower bound of the two-sided 95% CI on the difference in seroresponse rates between PXVX0317 and placebo groups (equivalent to a difference >0 using a two-sided chi-square test).

Note: Seroresponse rate (considered the presumptive seroprotection rate) is defined as the percentage of participants who achieve an anti-CHIKV SNA titer See Section 6.1 for assay description. See Section 8.6 for immunogenicity analysis details and Section 8.6.2.5 for success criteria and multiplicity controls.

• Anti-CHIKV SNA GMT and associated 95% CIs at Day 22 for PXVX0317 and placebo.

Success criterion: Significant difference in the IEP across all age groups combined using an ANOVA model with logarithmically transformed anti-CHIKV SNA titers (log₁₀) as the dependent variable and treatment group and study site as the fixed effects with a two-sided significance level of 0.05.

• Anti-CHIKV SNA GMT ratio between all three pairs of PXVX0317 lots (A:B, A:C, B:C) (adults 18 to <46 years of age) at Day 22.

Success criterion: Pairwise GMT ratios (A:B, A:C, B:C) each with a two-sided 95% CI within [0.667; 1.5] for the IEP in the 18 to <46 years of years of age stratum using an ANOVA model with log₁₀-transformed anti-CHIKV SNA titers as the dependent variable and vaccine lot and study site as the fixed effects to derive the GMT ratios.

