8.6 Immunogenicity Analysis

Summary statistics for immunogenicity results by scheduled visit for each treatment group will be provided for the IEP population, unless otherwise specified. In the analysis of the human SNA assay data as a continuous variable, anti-CHIKV SNA NT₈₀ values will be logarithmically transformed (base10), and the GMTs and associated 95% CI for each treatment group will be computed by exponentiating the corresponding log-transformed means and two-sided 95% CIs. Results will be presented for all age groups combined as well as separately. Geometric mean fold increase will also be displayed by postvaccination scheduled visit for each treatment group.

Proportions of participants with human SNA assay titer and secondary response rates at other titers (eg, 15 and 4-fold rise over baseline) will be reported with associated two-sided 95% Wilson method CIs by scheduled visit for each treatment group.

Reverse cumulative distribution plots of human SNA assay vs proportion of participants in each treatment group will be generated by scheduled visit. Geometric mean titer will also be plotted over time for each treatment group.

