8.6.1.2 Day 22 Geometric Mean Titer Analysis

In addition, Day 22 GMTs will be compared between PXVX0317 and placebo treatment groups and will be analyzed via a linear model based on an alpha=0.05. The primary model is an ANOVA, with logarithmically transformed anti-CHIKV SNA titers (log₁₀) as the dependent variable and treatment group and study site as the fixed effects in the model. The adjusted least square means and their 95% CIs calculated based on the ANOVA will be back transformed and reported as the group GMT values. All tests will be carried out at a two-sided significance level of 0.05 and no adjustment for multiplicity will be applied (see Section 8.6.2.5).

The primary comparison will be in the IEP across all age groups combined. Tests will be repeated in the mITT population as a measure of robustness, along with tests for each population in the separate age strata. No multiplicity adjustment will be made for the analysis of the separate age strata as the primary population will be the combined age groups.

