ANOVA with log₁₀-transformed anti-CHIKV SNA titers (log₁₀) as the dependent variable and treatment group and study site as the fixed effects. The adjusted least square means and their 95% CIs calculated based on the ANOVA are back-transformed and reported as the group GMT values. In standard statistical notation, the null and alternative hypotheses are:

H₀₂: $(GMT_{PXVX0317} - GMT_{placebo}) \leq 0$

HA2: $(GMT_{PXVX0317} - GMT_{placebo}) > 0$

where GMT_{PXVX0317} is the GMT 21 days after vaccination for IEP participants in all age strata pooled.

The third coprimary endpoint tests the pairwise GMT ratios at Day 22 of consecutively manufactured lots (A:B, B:C, A:C) for equivalence using two one-sided tests with alpha=0.025 each in the IEP for adults 18 to <46 years of age. Pairwise GMT ratios are derived from an ANOVA model with log₁₀-transformed anti-CHIKV SNA titers as the dependent variable and vaccine lot and study site as fixed effects. Lot-to-lot consistency is demonstrated if the two-sided 95% CI of the GMT ratio is within [0.667; 1.5] for all pairs of vaccine lots. In standard statistical notation, the null and alternative hypotheses are:

H₀₃: $(GMT_{PXVX0317 \text{ lot } A}/GMT_{PXVX0317 \text{ lot } B}) < 0.667 \text{ or}$

 $(GMT_{PXVX0317 \text{ lot } A} / GMT_{PXVX0317 \text{ lot } B}) > 1.5 \text{ or}$

 $(GMT_{PXVX0317 lot B}/GMT_{PXVX0317 lot C}) < 0.667 or$

 $(GMT_{PXVX0317 \text{ lot } B}/GMT_{PXVX0317 \text{ lot } C}) > 1.5 \text{ or}$

 $(GMT_{PXVX0317 \text{ lot } A} / GMT_{PXVX0317 \text{ lot } C}) < 0.667 \text{ or}$

 $(GMT_{PXVX0317 lot A}/GMT_{PXVX0317 lot C}) > 1.5$

H_{A3}: (GMT_{PXVX0317 lot A}/ GMT_{PXVX0317 lot B}) \geq 0.667 and

 $(GMT_{PXVX0317 \mbox{ lot }A}/\mbox{ }GMT_{PXVX0317 \mbox{ lot }B}) {\leq} 1.5$ and

 $(GMT_{PXVX0317 \mbox{ lot }B}/\mbox{ }GMT_{PXVX0317 \mbox{ lot }C}) \!\geq\!\! 0.667$ and

 $(GMT_{PXVX0317 \text{ lot }B}/GMT_{PXVX0317 \text{ lot }C}) \leq 1.5 \text{ and}$

 $(GMT_{PXVX0317 \text{ lot } A}/GMT_{PXVX0317 \text{ lot } C}) \ge 0.667 \text{ and}$

 $(GMT_{PXVX0317 \text{ lot } A}/GMT_{PXVX0317 \text{ lot } C}) \leq 1.5$

where GMT_{PXVX0317 lot X} is the GMT at 21 days after vaccination for IEP participants receiving PXVX0317 Lot A, B or C. Note that success on the Day 22 lot consistency endpoint is only required for FDA.

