8.4.2 Secondary Immunogenicity Endpoints

8.4.2.1 Key Secondary Immunogenicity Endpoints: Treatment Group Estimates and Difference in Anti-CHIKV SNA Seroresponse Rates at Day 15, Day 183, and Day 8, in that order

The key secondary endpoint of treatment-specific anti-CHIKV SNA seroresponse rates and treatment group difference in seroresponse rates (PXVX0317 minus placebo) and associated 95% CI based on antibody titers measured at Day 15, Day 183, and Day 8 is analyzed as described above for Day 22. For each time point, the null hypothesis of no difference between seroresponse rate percentages in the PXVX0317 vs placebo group is tested using a chi-square test with alpha=0.05. For Day 15 only, the lower bound of the two-sided 95% CI on the difference in seroresponse rates between PXVX0317 and placebo is compared to for assessment of clinical significance.

This endpoint is summarized for all age strata pooled and for individual age strata using the IEP. The analyses are repeated using the mITT population as a measure of robustness of results.

8.4.2.2 Anti-CHIKV SNA GMT at Day 8, Day 15, and Day 183 by Treatment Group

The secondary endpoint of anti-CHIKV SNA GMT and associated 95% CIs for PXVX0317 and placebo based on antibody titers measured at Day 8, Day 15, and Day 183 is analyzed as described above for Day 22.

This endpoint is summarized for all age strata pooled and for individual age strata using the IEP. The analyses are repeated using the mITT population as a measure of robustness of results.

8.4.2.3 GMFI in Anti-CHIKV SNA Titer from Day 1 to Days 8, 15, 22 and 183 by Treatment Group

Geometric mean fold increase over Day 1 (baseline) titer is analyzed as described for GMTs for each post-vaccination time point (Days 8, 15, 22 and 183) by treatment group. See Section 6.1 for statistical details and Section 6.3 for handling of anti-CHIKV SNA titer values below LLOQ.

This endpoint is summarized for all age strata pooled and for individual age strata using the IEP population. Geometric mean fold increase is plotted by visit for the IEP, and a reverse cumulative distribution of fold-rise from baseline by visit is also presented for the IEP.

8.4.2.4 Participants with Anti-CHIKV SNA Titer ≥15 and 4-fold Rise over Baseline at Days 8, 15, 22 and 183 by Treatment Group

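### The group GMT and GMFI confidence intervals use one residual variance for both arms, although the placebo arm should have far less spread than the vaccine arm; only reported precision is affected

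*SAP*

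**What the plan says.** The second coprimary endpoint is the Day 22 GMT with its 95% CI in each arm. Protocol 8.6.1.2 fits an ANOVA to log10 titers with "treatment group and study site as the fixed effects in the model", and SAP 6.4.1 repeats "treatment group and study site as the fixed effects" for the formal hypothesis. SAP 6.1.2 then says what is printed: "The adjusted least square means and their 95% CIs calculated based on the ANOVA are back-transformed and reported as the group GMT values". The Protocol synopsis, Protocol 8.6.1.2 and SAP 6.4.1 say the same. No robust, arm-specific or unequal-variance option appears, so the usual single residual variance applies.

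The same model serves GMFI (SAP 6.1.2: "95% CIs calculated based on the ANOVA are backtransformed and reported as the group GMFI values") and the later and earlier visits (SAP 8.4.2.2: "based on antibody titers measured at Day 8, Day 15, and Day 183 is analyzed as described above for Day 22"), and it is repeated in each age stratum.

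Success depends on the test, not on the group intervals. Protocol 8.3.1 has: "Success criterion: Significant difference in the IEP across all age groups combined using an ANOVA model".

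The general text describes a simpler interval. Protocol 8.6 says "the GMTs and associated 95% CI for each treatment group will be computed by exponentiating the corresponding log-transformed means and two-sided 95% CIs", and SAP 6.1 has the same sentence in the present tense.

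**The concern.** One residual variance is reasonable when the arms have similar spread. Here the plan's own rules point the other way. SAP 5.3 restricts the IEP to participants below LLOQ at baseline. SAP 6.3 replaces every titer below LLOQ by the constant LLOQ/2. SAP 4.1 expects placebo seroresponse below 5% and uses 0% in its precision calculation. Most placebo values should therefore be one substituted number, while the planning SD for vaccinees is 0.455.

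With 6:1 allocation the vaccine arm dominates the pooled variance. The pooled SD is then slightly too small for the vaccine arm and much too large for placebo. What is at stake is whether the printed intervals, which form part of a coprimary endpoint, describe the precision of the arm they are attached to.

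**Working it through.** **Inputs from the documents.** Vaccine SD of log10 titer 0.455 (SAP 4.2; the upper bound of an 80% CI, so conservative). Evaluable numbers 2430:405 overall and 189:32 in each small age stratum (SAP 4.1). Earlier single-dose GMT 1712 at 28 days (Protocol 1.3.2), used only for scale.

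**Assumptions.** The documents give no placebo SD and no LLOQ value. I take placebo SD 0 to 0.2 and, where a titer scale is needed, LLOQ = 15.

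**The plan's own figure.** Lot-equivalence power with SD 0.455, 207 per lot and margin ±0.176 is 2Φ(0.176/(0.455√(2/207)) − 1.96) − 1 = 95.2%, against 95% stated. The SD input is used as the plan intends.

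**Pooled SD.** s_p = √{[(n1−1)s1² + (n0−1)s0²]/(n1+n0−2)}. Overall this is 0.421 for s0 = 0 and 0.428 for s0 = 0.2.

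**Intervals without sites.** The half-width is t·s/√n on the log10 scale, then back-transformed. Vaccine coverage is 2Φ(t·s_p/0.455) − 1.

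| | Pooled variance | Own variance | Vaccine coverage |
|---|---|---|---|
| Vaccine, 2430 | ×/÷1.039–1.040 | ×/÷1.043 | 93.1%–93.5% |
| Placebo, 405 | ×/÷1.10 | ×/÷1.00–1.05 | |
| Vaccine, 189 | ×/÷1.149–1.152 | ×/÷1.162 | 93.2%–93.6% |
| Placebo, 32 | ×/÷1.40–1.41 | ×/÷1.00–1.18 | |

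At a GMT of 1712 and placebo SD 0, the overall vaccine limits are 1647–1779 (pooled) against 1642–1785 (own), a shift of about 0.3%. If every placebo value were 7.5, the pooled stratum interval would be about 5.3–10.5. Its lower limit would lie below LLOQ/2, and all of its width would come from vaccinees. The placebo comparison is with the spread of the substituted values, not of true titers below LLOQ.

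**GMFI.** In the IEP every baseline value is LLOQ/2, so log fold increase is log titer minus a constant and the same widths apply.

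**With sites.** Simulations of the planned model (assumed site sizes and between-site differences) gave vaccine coverage of 92.3%–94.5%. The unadjusted vaccine-arm interval gave 93.7%–96.0%; in one scenario both covered 93.7%.

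**The test.** Overall, the pooled SE of the difference is 0.0226–0.0230, against 0.0092–0.0136 allowing unequal variances. The critical difference is about 0.044–0.045 log10. The expected difference is about log10(1712/7.5) = 2.36.

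**Where it reverses.** Let a share q of placebo have vaccine-like titers (GMT 1712, SD 0.455) and the rest sit at 7.5. The arm variances are equal when q·0.455² + q(1−q)·2.358² = 0.455², that is q = 3.7%. At q = 5% the placebo SD is 0.52.

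**The case against.** The strongest reply is that this is immaterial. The success criterion is a conservative test, and the vaccine limits barely move. The plan also shows the placebo distribution directly, through reverse cumulative plots, Wilson intervals for response rates, and median, minimum and maximum titers. This stands, and it is why the point is low severity.

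The inputs are also partly assumed. Placebo SD, LLOQ and site sizes are not given, and 0.455 is an upper bound. That stands as well, but the conclusion is not sensitive to the vaccine SD: at an assumed 0.35, with placebo SD 0.10, the overall placebo interval is still about 3.3 times too wide on the log scale.

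Site weighting can matter more than the variance. If least-squares means weight sites equally, the planned vaccine half-width was 0.018–0.028 log10 overall and 0.073–0.087 in strata, against 0.018 and 0.065 unadjusted. An own-variance interval is therefore not always wider.

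A reader might infer from Protocol 8.6 and SAP 6.1 that the documents leave open which interval is reported. They do not: the GMT sections and SAP 6.4.1 name the ANOVA intervals, and the general sentences can be read alongside them.

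**Conclusion.** The concern holds for reported precision only. Under the stated assumptions, the vaccine GMT interval covers about 93%–94% rather than 95%, and the placebo interval mainly reflects vaccine variability, most visibly in the small age strata. The result rests on placebo titers lying mostly below LLOQ. It would reverse only if roughly 4% or more of placebo participants had vaccine-like titers, which is unlikely in a baseline-seronegative US population.

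A reader might infer that a coprimary decision is at risk. The documents do not support that. The pooled SE overstates the error of the treatment difference, so the superiority test is conservative. The lot-consistency model in SAP 6.1.2 contains vaccine lots only. The seroresponse comparisons are on proportions.

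**What to change.** - Keep the treatment-plus-site ANOVA for the superiority test.
- Report each arm's GMT and GMFI with a 95% CI from that arm's own log10 mean and variance, as Protocol 8.6 and SAP 6.1 already describe for GMTs, beside or in place of the least-squares-mean interval.
- Amend the synopsis text on superiority at Day 22, Protocol 8.6.1.2, SAP 6.1.2 and SAP 6.4.1 together, so that all name the same reported interval. Days 8, 15 and 183 follow by reference.
- Keep a placebo CI, since the endpoints require one. Where most placebo values are below LLOQ, add a footnote that the GMT is largely a substituted value, and show the percentage below LLOQ with its Wilson CI (the method already in SAP 6.1.1).

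The cost is wording and one extra output column. The vaccine interval becomes 6%–8% wider on the log scale than the pooled-variance interval with no sites or with participant-weighted sites, and possibly narrower than the least-squares-mean interval if sites are weighted equally. An own-data placebo interval can collapse in a small stratum: if 2.5% of placebo participants are quantifiable, 0.975^32 = 44.5% of samples of 32 have none and zero variance. That is why the footnote and Wilson interval are needed.
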